5 ANALYSES POPULATION

Agreement and authorization of patients included/excluded from each analysis Population will be performed on a case-by-case basis before the database lock/un-blinding.

5.1 ALL PATIENTS ENROLLED [ENR]

The Enrolled (ENR) population will contain all patients who provided informed consent for this study.

The Enrolled (ENR) population will be used for the Patient disposition Table and Listings. And it will be analysed according to the randomized treatment, if applicable.

5.2 RANDOMIZED POPULATION [RND]

The Randomized (RND) population will contain all patients in the ENR Population who were randomized to the study, regardless of whether they received study medication or not. Patients will be analysed according to the treatment they were randomized.

5.3 FULL ANALYSIS SET [FAS]

The Full Analysis Set (FAS) population will consist of all randomized patients who received at least one dose of the study medication (either Raloxifene or Placebo).

The Full Analysis Set (FAS) population will be used for Primary and secondary efficacy analyses, all the demographics and baseline characteristics Tables and Figures. Patients will be analysed according to the treatment they were randomized.

5.4 SAFETY POPULATION [SAF]

The Safety (SAF) population will consist of all randomized patients who received at least one dose of the study medication.

The Safety (SAF) population will be used to present results on safety data. Safety data will be analysed according to the treatment which patients have received.

5.5 PER PROTOCOL POPULATION [PP]

The Per Protocol (PP) population will consist of all randomized patients who received at least one dose of the study medication and do not have any Major Protocol Deviations.

The Per Protocol (PP) population will be used for sensitivity analyses of the efficacy endpoints. Patients will be analysed according to the treatment they were randomized.

6 PROTOCOL DEVIATIONS

All the protocol deviations will be discussed on a case by case basis by the clinical team prior to database lock. Any significant deviation from the protocol will be

reviewed and a decision taken regarding evaluation for each analysis population.

7 GENERAL CONSIDERATIONS

7.1 REFERENCE START DATE AND STUDY DAY

In general, reference start date is defined as the day of the first dose of study medication (Study Day 1: first day) and will appear in every listing where an assessment date or event date appears.

Study Day will be calculated from the reference start date and will be used to show start / stop day of assessments and events.

If the date of the assessment/event is on or after the reference start date, then:

Study Day = (date of assessment/event – reference start date) + 1

If the date of the assessment/event is prior to the reference start date, then:

Study Day = (date of assessment/event – reference start date)

In the situation where the assessment/event date is partial or missing, the date will appear partial or missing in the listings, and Study Day and any corresponding duration will be presented based on the imputations specified in Appendix 2 (Partial Date Conventions).

7.2 STUDY BASELINE AND POST BASELINE

7.2.1 BASELINE

Unless otherwise specified, study baseline is defined as the last non-missing measurement taken prior to first IMP administration.

7.2.2 POST-BASELINE

Post-Baseline is defined as the measurement taken after the first IMP administration.

7.2.3 CHANGE FROM BASELINE

For some quantitative measurements, change from baseline will be calculated as:

Change from baseline = Value at Post-Baseline Visit – Baseline Value

7.3 EARLY WITHDRAWAL FROM THERAPY OR ASSESSMENT AND END OF STUDY

7.3.1 EARLY TRIAL DISCONTINUATION VISIT AND UNSCHEDULED VISITS

In general, for by-visit summaries, data recorded at the nominal visit will be presented.

Unscheduled measurements will not be included in by-visit summaries. Listings will include scheduled, unscheduled, and early trial discontinuation visit (ETDV).

7.3.2 PREMATURE DISCONTINUATION

A premature discontinuation will occur when a patient who signed the ICF ceases participation in the study, regardless of circumstances, before the completion of the study protocol procedures. Patients can be prematurely discontinued from the study for one of the following reasons:

Primary Reason for treatment discontinuation:

- Failure to meet inclusion/exclusion criteria or severe protocol violations
- Negative Nasopharyngeal swab
- Withdrawal of consent
- Lost to follow-up
- Study terminated by the Sponsor
- Documented disease progression
- Development of AE or unacceptable toxicity, precluding further therapy with the study drug
- Pregnancy
- Hypoalbuminemia at a level considered clinically relevant by the investigator
- Other reasons

Primary Reason for study discontinuation:

- Failure to meet inclusion/exclusion criteria or severe protocol violations
- Withdrawal of consent
- Lost to follow-up (Every effort must be made to contact the patient; a registered letter must be sent)
- Study terminated by the Sponsor
- Development of AE or unacceptable toxicity, precluding further therapy with the study drug
- Pregnancy
- Other reasons

In case of discontinuation, patients will undergo a remote Early Trial Discontinuation Visit aimed to assess physical abnormalities, vital signs and transdermal oxygen saturation measurement.

7.3.3 END OF STUDY (EOS)

The EOS is defined as the last day the last patient completes the last study assessment, or retracts the consent to participate in the study, or withdraws from the study, or is deceased or otherwise lost to follow-up.

7.4 ALL LISTINGS

All data will be listed by the patient.

7.5 SOFTWARE VERSION

All statistical analyses will be conducted using the SAS® System version 9.1.3 or higher.

8 STATISTICAL METHODOLOGY AND CONSIDERATIONS

8.1 ADJUSTMENTS FOR COVARIATES AND FACTORS TO BE INCLUDED IN ANALYSES

In the analysis of primary endpoints and secondary endpoints, the following factors/covariates will be considered in the Binary Logistic regression and Repeated Measures Logistic regression model as described in the SAP section 14.1

- Treatment group;
- Center;
- Age group;
- Status (Male, Female pre-menopausal status, Female post-menopausal status);
- For Clinical outcome: Baseline NEWS value.

8.2 MULTICENTRE STUDIES

This study will be conducted by multiple investigators at multiple centres and randomization will be stratified by site and gender. Both stratification factors will be included in the primary efficacy analysis model.

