3.2. STUDY ADMINISTRATIVE STRUCTURE

This study will be performed in clinical centers located in Europe (Italy, France, Spain). At each study center, the Principal Investigator (PI) will be responsible for ensuring that the investigation is conducted according to the signed Investigator agreement, the protocol, GCP guidelines, and local regulations.

The PI at each study center will be responsible for the management of the study, which will consist of maintaining the study file and the patient records, corresponding with the IRB/IEC, and completing the electronic case report form (eCRF) and reporting SAEs within 24 hours of initial awareness.

The PI is responsible for supervising any individual or party to whom the investigator delegates trial related duties and functions conducted at the trial site. If the investigator/institution retains the services of any individual or party to perform trial-related duties and functions, the investigator/institution should ensure this individual or party is qualified to perform those trial-related duties and functions and should implement procedures to ensure the integrity of the trial-related duties and functions performed and any data generated.

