4.3 INTERIM ANALYSIS

An interim analysis was planned for this study when half (i.e 50 participants per arm (N=150)) of the planned evaluable patients would have reached the primary endpoints at 7 and 14 days (i.e., assessments available).

The intent of the interim analysis was either for identification of early superiority of raloxifene (early efficacy), or for an early stop of one or both treatment arms for futility, or for blind sample size reassessment.

Due to the premature interruption of the enrolment (with 68 patients included in the study), no interim analysis will be done.

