14 ANALYSES OF EFFICACY VARIABLES

14.1 EFFICACY ANALYSES

NEWS score evaluation will be performed at T0, T7, T14 and T28. NEWS score and NEWS score parameters as per collected in CRF will be provided in Listing for FAS population. Refer Appendix 3 for NEWS score.

Table 3: Summary of Analyses Strategies for efficacy endpoints:

Endpoint	Analysis set	Statistical method	Factors/Co variates	Missing data Handling	Analyses type
Virologic outcome - Proportion of patients with undetectable SARS-CoV-2 at PCR at day 7 after randomization.	FAS	Binary Logistic regression	Treatment, center, age and status	Missing data will not be imputed	Primary analysis
Virologic outcome - Proportion of patients with undetectable SARS-CoV-2 at PCR at day 7 after randomization.	PP	Binary Logistic regression	Treatment, center, age and status	Missing data will not be imputed	Sensitivity analysis
Clinical outcome - Proportion of patients who does not require supplemental oxygen therapy (NEWS ≤2) and/or mechanical ventilation at day 14 after randomization.	FAS	Binary Logistic regression	Treatment, center, age, status and baseline NEWS	Missing data will not be imputed	Primary analysis
Clinical outcome - Proportion of patients who does not require supplemental oxygen therapy (NEWS ≤2) and/or mechanical ventilation at day 14 after randomization.	PP	Binary Logistic regression	Treatment, center, age, status and baseline NEWS	Missing data will not be imputed	Sensitivity analysis

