14.1.1 PRIMARY EFFICACY ENDPOINTS AND ANALYSES

1. Proportion of patients with undetectable SARS-CoV-2 at PCR at day 7 after randomization (virologic endpoint). This endpoint will be derived as below.
 - Based on Approved molecular test (PCR) result at day 7, the responses will be considered as “detectable” if PCR result is “Positive” otherwise “undetectable” if PCR result is “Negative” (Missing PCR result will be considered as missing in the main analysis).

The response (detectable / undetectable) at day 7 will be analysed using Binary logistic regression model with treatment group and pre-defined baseline factors (center, age, status and their interaction effects with treatment group). Odds ratio

will be computed for comparisons of each active treatment group versus placebo. i.e., raloxifene (60 mg) versus placebo and raloxifene (120 mg) versus placebo.

2. The proportion of patients who does not require supplemental oxygen therapy (NEWS ≤ 2) and mechanical ventilation at day 14 after randomization (clinical endpoint). This endpoint will be derived as below.

- If collected NEWS score > 2 or mechanical ventilation at day 14 result “Yes” then the response will be considered as “Required”. If collected NEWS score ≤ 2 and mechanical ventilation with result “No” then the response will be considered as “Not Required” (if both NEWS score and mechanical ventilation are missing, patient will be considered as missing).

The response (Required/ Not required) at day 14 will be analysed using Binary logistic regression model with treatment group and pre-defined baseline factors (center, age, status, baseline NEWS and their interaction effects with treatment group). Odds ratio will be computed for comparisons of each active treatment group versus placebo. i.e., raloxifene (60 mg) versus placebo; and raloxifene (120 mg) versus placebo.

For both virologic and clinical endpoint, Binary Logistic regression will be performed using PROC GENMOD in SAS® on the observed data only to estimate difference in proportions between each active treatment versus placebo and its corresponding 95% (2-sided) confidence intervals. Exponential transformation will be used to obtain the odds ratio and corresponding 95% confidence interval. P-values will be reported based on the Wald tests from Type III analyses. Bonferroni method will be considered to handle multiple treatment comparisons.

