In the SAS® procedure PROC GENMOD, a Type III analysis will be performed by adding the model options: TYPE3, DIST=BIN and LINK=LOGIT.

If the model does not converge then the following steps will be performed subsequently:

- PROC GENMOD with EXACT statement will be used.
- If the model still does not converge, then remove the factors/covariates from the model one by one (according to statistical significance) until convergence reached.
- If the model still does not converge, then perform the Fisher's exact using the SAS procedure PROC FREQ without adjusting for any pre-defined factor and covariates.

The following hypotheses will be tested:

- The null hypothesis for the virologic endpoint is that proportion of treated patients with undetectable SARS-CoV-2 at PCR at day 7 after randomization ($\pi_{RALOXIFENE}$) is lower or equal the placebo one ($\pi_{PLACEBO}$). Two sets of null and alternative hypotheses are provided, one for each treatment dosage:

$$H_{01-60mg}: \pi_{RALOXIFENE-60mg} \leq \pi_{PLACEBO}$$

$$H_{11-60mg}: \pi_{RALOXIFENE-60mg} > \pi_{PLACEBO}$$

$$H_{01-120mg}: \pi_{RALOXIFENE-120mg} \leq \pi_{PLACEBO}$$

$$H_{11-120mg}: \pi_{RALOXIFENE-120mg} > \pi_{PLACEBO}$$

- The null hypothesis for the clinical endpoint is that proportion of treated patients who does not require supplemental oxygen therapy (NEWS ≤ 2) and/or mechanical ventilation at day 14 after randomization ($T_{RALOXIFENE}$) is lower or equal the placebo one ($T_{PLACEBO}$). Two sets of null and alternative hypotheses are provided, one for each treatment dosage:

$$H_{02-60mg}: T_{RALOXIFENE-60mg} \leq T_{PLACEBO}$$

$$H_{12-60mg}: T_{RALOXIFENE-60mg} > T_{PLACEBO}$$

$$H_{02-120mg}: T_{RALOXIFENE-120mg} \leq T_{PLACEBO}$$

$$H_{12-120mg}: T_{RALOXIFENE-120mg} > T_{PLACEBO}$$

Superiority of raloxifene will be established if at least one null hypothesis is rejected.

The frequency and percent will be presented by treatment and visit for both primary endpoints results.

The following figures will be produced for both primary endpoints results:

- Bar chart for Proportion of Patients with undetectable SARS-CoV-2 at PCR by treatment and visit
- Bar chart for Proportion of Patients who does not require supplemental oxygen therapy (NEWS ≤ 2) and/or mechanical ventilation by treatment and visit

The following listings will be presented:

- Listing for the Nasopharyngeal Swab Test (PCR) results
- Listing for the supplemental oxygen therapy (NEWS ≤ 2) and/or mechanical ventilation

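### With 68 patients, unpenalised logistic regression with a term for every centre overstates the primary odds ratios; separately, its Wald test cannot reject if a dose arm has no clinical failure

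*SAP*

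**What the plan says.** SAP 4.3 reports that recruitment ended early "with 68 patients included in the study". SAP 4.1.2 had expected 250 to 450.

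The primary model was not reduced to match:
- **Centre.** SAP 8.2 states of the randomisation factors, site and gender, that "Both stratification factors will be included in the primary efficacy analysis model". Gender enters through the three-level status variable.
- **Covariates.** Table 3 in SAP 14.1 lists, for the clinical endpoint, "Treatment, center, age, status and baseline NEWS". The virologic model is the same without baseline NEWS. SAP 14.1.1 words it more broadly, as "pre-defined baseline factors (center, age, status and their interaction effects with treatment group").
- **Estimation.** In SAP 14.1.1, "a Type III analysis will be performed by adding the model options: TYPE3, DIST=BIN and LINK=LOGIT". P-values are Wald, and "Exponential transformation will be used to obtain the odds ratio and corresponding 95% confidence interval". No penalty, conditioning, random centre effect or pooling of small centres is specified.
- **Fallback.** If the fit fails to converge, SAP 14.1.1 moves to exact logistic regression, then to removing covariates one at a time by significance, then to an unadjusted Fisher test.

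**The concern.** Maximum likelihood for a logistic model pushes log odds ratios away from zero when there are few patients per parameter. A factor with a level for every centre is a common cause. A centre where all patients have the same outcome adds nothing to the treatment estimate, so the effective sample is smaller than 68. The reported odds ratio would then be too large for purely numerical reasons, in a trial whose main remaining use is to describe the effect.

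The second issue is separate. If no patient on a dose fails clinically, the log odds ratio has no finite estimate, its standard error diverges and the Wald Z goes to zero. The strongest possible result for that arm would be reported as non-significant.

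**Working it through.** **1. Significance level.** The protocol's Pocock boundary (9.3, Table 1) is 2.69640. Solving P(Z1 > c or Z2 > c) = 0.025/4 with correlation √0.5 gives c = 2.6964, which reproduces it. The Bonferroni split is therefore over four tests (two doses, two endpoints), 0.00625 one-sided each. I assume a single look, since the interim was cancelled, so z = 2.498.

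**2. Parameters against data.** Take K centres, two age groups and three status levels. The virologic model has 1 + 2 + (K−1) + 1 + 2 = K + 5 parameters, and the clinical model K + 6. With 68/3 = 22.7 per arm and both doses at the planned rates:
- expected negative swabs: 22.7 × (0.25 + 0.50 + 0.50) ≈ 28
- expected clinical failures: 22.7 × (0.50 + 0.25 + 0.25) ≈ 23

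| K | Virologic: parameters, negatives per parameter | Clinical: parameters, failures per parameter |
|---|---|---|
| 3 | 8, 3.5 | 9, 2.5 |
| 15 | 20, 1.4 | 21, 1.1 |

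K is an assumption. Protocol 3.2 says only "This study will be performed in clinical centers located in Europe (Italy, France, Spain").

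**3. Bias of the odds ratio.** The documents give no figure, so it was simulated: 68 patients, three arms, main effects only, unequal centre sizes, centre SD 0.5 on the logit, 600 runs per cell, and the planned rates (25% to 50% and 50% to 75%, both a true odds ratio of 3).

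| Centres | Median ML odds ratio | At least one coefficient separated |
|---|---|---|
| 3 | 3.5-3.8 | 6-9% |
| 6 | 3.6-3.8 | 36-46% |
| 10 | 4.2-4.3 | 85-92% |
| 15 | 4.4-4.9 | 99-100% |

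The mean finite log odds ratio is 1.20-1.28 times the truth with 3-6 centres and 1.39-1.51 times with 10-15. Firth with the same covariates gives medians of 2.9-3.1. A second simulation with centre SD 0.3 and 8-15 centres gave 4.1-4.2 for ML on the virologic endpoint. A further check put Firth at up to 3.2.

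**4. Wald test, unadjusted, 23 per arm.** This needs no centre terms.
- *11 placebo failures against 1.* Log odds ratio = ln[(11 × 22)/(1 × 12)] = 3.00; SE = √(1/11 + 1/12 + 1/1 + 1/22) = 1.10; Z = 2.72; one-sided p = 0.0033. It rejects at 0.00625.
- *11 against 0.* The estimate is infinite and the Wald p is near 1. Fisher's two-sided p is 0.0002 and the likelihood-ratio p is 0.00001.

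With covariates, 3-10 centres and 11 placebo failures, Wald rejects in 0% of runs at 0 dose failures, 89-96% at 1 and 85-88% at 2.

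**5. Chance of a dose arm with no failure, 23 per arm.** For either active arm it is 1 − (1 − s^23)^2, where s is the success rate.
- s = 0.75 (planned): 0.75^23 = 0.0013, so 0.3%
- s = 0.90: 0.90^23 = 0.089, so 17%

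**6. Power and null behaviour.** At the planned odds ratio of 3, power is about 16-22% under either ML Wald or Firth. Firth's null rejection at 0.00625 was 0.1-0.7%.

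**7. Interactions.** With the treatment interactions of SAP 14.1.1 at planned rates (200 runs, 3-10 centres, 18-39 parameters), the treatment coefficient was infinite in 39-95% of runs and Wald rejected in 0-0.5%. These figures depend on factor coding.

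**The case against.** Four arguments deserve weight.

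*The SAP already has exact methods.* If zero failures were flagged as non-convergence, the ladder would repair the test, as the Fisher p of 0.0002 for 11 against 0 shows. This stands in part. The SAP does not say that separation is a trigger, and software can report convergence with a very large standard error. The ladder never acts on a converged but inflated estimate.

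*The bias is small beside the imprecision.* At 25% v 50% with 23 per arm, the unadjusted SE of the log odds ratio is 0.64. A shift from 3 to 4.15 is ln(4.15/3) = 0.32, half of that. SAP 14.1.1 also tabulates raw percentages by arm. Both are true, but the model's odds ratio remains the reported effect and its bias is avoidable.

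*The number of centres is unknown.* This stands for the size. The direction holds at every count tried, including three.

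*Firth is not perfect.* At 80% v 90% success (true odds ratio 2.25) it gave 2.0-2.1, slightly low, against 3.2-3.4 for ML.

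A reader might also infer that the centre terms cause the Wald failure, or that the test is nearly blind whenever a dose prevents almost all failures. The figures do not support either. The failure appears in a plain 2×2 table, and with one or two dose failures against 11 the test still rejects in 85-96% of runs.

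**Conclusion.** The concern holds for estimation. The first-line primary model overstates the log odds ratio by roughly 20-50% over 3 to 15 centres, even in the main-effects form of Table 3. The size rests on an assumed centre count, unequal centre sizes and modest variation between centres.

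It holds conditionally for testing. The Wald test fails with zero failures in an active arm, which is remote under the planned 75% success and a real possibility only if success is nearer 90%. The documents plan 50% to 75%, so high success rates are a sensitivity case and not the plan's expectation. They do not settle whether the fallback would then start.

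A reader might expect penalisation to rescue power. It does not at the planned effect. Adjusting for the stratification factors is not itself an error; the problem is how the model is fitted in so few patients. The change is worthwhile because it is cheap.

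**What to change.** In SAP 14.1.1, before unblinding:
- Fit both primary models by Firth penalised likelihood (PROC LOGISTIC with FIRTH and profile-likelihood limits), main effects only. This also removes the disagreement with SAP 8.1 and Table 3 over interactions.
- Report penalised likelihood-ratio p-values and profile intervals for each dose against placebo.
- Pool centres below a stated size within their country. Pooling alone is not enough, because the ML bias is present with three centres.
- If the GENMOD ladder is kept as a sensitivity analysis, state that complete or quasi-complete separation triggers it.

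The cost is SAP wording and a change of procedure. The downside is slight shrinkage of the estimates and coarser adjustment for the smallest centres.

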8.3 SENSITIVITY AND SUPPORTIVE ANALYSES

The virologic and clinical primary efficacy endpoints will be analysed using the same Binary Logistic regression procedure given in SAP section 14.1.1 on PP Population using observed data only; these analyses will be performed to explore the robustness of the primary results versus protocol adherence.

8.4 MULTIPLE COMPARISONS/ MULTIPLICITY

Bonferroni method is used to adjust for multiple endpoints and treatment comparisons.

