9. STATISTICS

9.1. SAMPLE SIZE

The sample size of the study is calculated based on the following assumptions:

- Virologic assumption: Early treatment with antivirals increases the proportion of patients with undetectable SARS-CoV-2 in upper respiratory tract at day 7 after therapy from 25% to 50%;
- Clinical assumption: Early treatment with antivirals increases the proportion of participants who recover without need of mechanical ventilation and/or supplemental oxygen therapy by the day 14 after therapy from 50% to 75%.

Based on these assumptions and considering a randomization ratio 1:1:1, the sample size will be adaptively determined to achieve a power greater than 80% to show superiority of raloxifene vs placebo in terms of either one primary endpoint (section 7.1.1) and controlling the one-sided alpha below 0.025.

Sample size will be determined through the following steps:

- an interim analysis will take place when 50 participants per arm (N=150) have reached their primary endpoints (i.e. assessments available).
 - In case of efficacy of at least one treatment arm or futility of both arms (see criteria in section 9.3) the study enrolment will be stopped,
 - otherwise the actual number of new participants in each arm may be blindly reassessed according to observed efficacy of the best favourable and promising arm;
- in case of continuation of the study to the final stage, it is expected to randomize on average additional 174 patients, depending on sample size reassessment and possible dropping of an ineffective treatment arm. Expected sample size will be between 250 and 450 randomized participants;
- drop-outs of randomized subjects will not be replaced.

This approach allows either to minimize the number of enrolled participants if the experimental assumptions are too conservative or to have a good power level if they are too optimistic.

Pocock's spending functions and conditional power (CP) will be used to control the type I and II errors, considering that interim analysis will be performed when half of the initial planned patients have been reached the primary endpoints (i.e. assessments available).

Bonferroni method is used to adjust for multiple endpoint vs treatment comparisons.

Sample size calculation has been performed through simulation (100000 replications). The statistical software used for simulation was SAS®, Version 9.4.

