9.5.2. Analysis of efficacy variables

9.5.2.1. Primary analyses

The proportion of subjects with undetectable SARS-CoV-2 at PCR at day 7 after randomization (virologic endpoint) and the proportion of subjects who not requires supplemental oxygen therapy (NEWS ≤ 2) and/or mechanical ventilation at day 14 after randomization (clinical endpoint) will be separately analyzed by means of logistic regression models adjusting by pre-defined factors as center, age, gender and post-menopausal status. Additional covariates may be defined in the SAP. Each treatment arm will be compared independently with the placebo.

The null hypothesis for the virologic endpoint is that proportion of treated subjects with undetectable SARS-CoV-2 at PCR at day 7 after randomization is lower or equal the placebo one ($\pi_{PLACEBO}$). Two sets of null and alternative hypotheses are provided, one for each treatment dosage:

$$H_{01-60mg}: \pi_{RALOXIFENE-60mg} \leq \pi_{PLACEBO}$$

$$H_{01-120mg}: \pi_{RALOXIFENE-120mg} \leq \pi_{PLACEBO}$$

$$H_{11-60mg}: \pi_{RALOXIFENE-60mg} > \pi_{PLACEBO}$$

$$H_{11-120mg}: \pi_{RALOXIFENE-120mg} > \pi_{PLACEBO}$$

The null hypothesis for the clinical endpoint is that proportion of treated subjects who not requires supplemental oxygen therapy (NEWS ≤ 2) and/or mechanical ventilation at day 14 after randomization is lower or equal the placebo one ($\pi_{PLACEBO}$). Two sets of null and alternative hypotheses are provided, one for each treatment dosage:

$H_{02-60mg}: T_{RALOXIFENE-60mg} \leq \pi_{PLACEBO}$ $H_{02-120mg}: T_{RALOXIFENE-120mg} \leq \pi_{PLACEBO}$ $H_{12-60mg}: T_{RALOXIFENE-60mg} > \pi_{PLACEBO}$ $H_{12-120mg}: T_{RALOXIFENE-120mg} > \pi_{PLACEBO}$

Superiority of raloxifene will be claimed if at least one null hypothesis is rejected, at interim or at final analysis according to criteria shown in section 9.3.

Sensitivity analyses will be defined in the SAP to assess the robustness of results on primary endpoints versus the presence of missing data (unexpected) and the presence of protocol deviations.

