4.1.2 SAMPLE SIZE

The sample size of the study has been based on the following assumptions:

- Virologic assumption: Early treatment with antivirals increases the proportion of patients with undetectable SARS-CoV-2 in upper respiratory tract at day 7 after therapy from 25% to 50%.
- Clinical assumption: Early treatment with antivirals increases the proportion of

patients who recover without need of mechanical ventilation and/or supplemental oxygen therapy by the day 14 after therapy from 50% to 75%.

Based on these assumptions and considering a randomization ratio 1:1:1, the sample size will be adaptively determined to achieve a power greater than 80% to show superiority of raloxifene vs placebo in terms of either one of primary endpoint and controlling the one-sided alpha below 0.025.

Sample size will be determined through the following steps:

- an interim analysis will take place when 50 patients per arm (N=150) have reached their primary endpoints (i.e. assessments available).
 - In case of efficacy of at least one treatment arm or futility of both arms (see criteria in protocol section 9.3) the study enrollment will be stopped,
 - otherwise the actual number of new patients in each arm may be blindly reassessed according to observed efficacy of the best favourable and promising arm;
- in case of continuation of the study to the final stage, it is expected to randomize on average additional 174 patients, depending on sample size reassessment and possible dropping of an ineffective treatment arm. Expected sample size will be between 250 and 450 randomized patients;
- drop-outs of randomized subjects will not be replaced.

This approach allows either to minimize the number of enrolled patients if the experimental assumptions are too conservative or to have a good power level if they are too optimistic.

Pocock's spending functions and conditional power (CP) will be used to control the type I and II errors, considering that interim analysis will be performed when half of the initial planned patients have been reached the primary endpoints (i.e. assessments available).

Bonferroni method is used to adjust for multiple endpoint vs treatment comparisons. Sample size calculation has been performed through simulation (100000 replications). The statistical software used for simulation was SAS®, Version 9.4.

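### Holm would give more power than single-step Bonferroni for the second and later dose-by-endpoint hypotheses at the same one-sided 0.025; the plan's main claim is unaffected

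*SAP*

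**What the plan says.** Protocol 9.1 sets the multiplicity rule as "Bonferroni method is used to adjust for multiple endpoint vs treatment comparisons", and SAP 8.4 repeats it as "Bonferroni method is used to adjust for multiple endpoints and treatment comparisons". SAP 14.1.1, where the primary models are specified, is narrower: "Bonferroni method will be considered to handle multiple treatment comparisons". That sentence does not mention endpoints.

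For each primary endpoint, SAP 14.1.1 says "Two sets of null and alternative hypotheses are provided, one for each treatment dosage". Two endpoints and two doses make four one-sided null hypotheses. The conclusion drawn from them is a single one: "Superiority of raloxifene will be established if at least one null hypothesis is rejected". Protocol 9.5.2.1 has the same rule ("Superiority of raloxifene will be claimed if at least one null hypothesis is rejected"). The design aims, in SAP 4.1.2, "to achieve a power greater than 80% to show superiority of raloxifene vs placebo" on either one of the primary endpoints, while "controlling the one-sided alpha below 0.025".

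No step-down, gatekeeping or other sequential procedure is described. SAP 4.3 records that enrolment stopped at 68 patients and that the interim analysis will not be done. SAP 18 lists the cancelled interim as a change from the protocol and has no entry on multiplicity.

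**The concern.** The success rule needs only one rejection, but the plan sets out to learn more. Its objective is to evaluate two doses, the virologic and clinical questions are separate primary objectives, and Protocol 9.5.2.1 compares each dose with placebo on its own. Which dose worked, and on which endpoint, depends on the second, third and fourth hypotheses. Single-step Bonferroni keeps the full penalty on these after others have been rejected. Holm relaxes the penalty step by step at the same overall error. What is at stake is power for these additional dose-level and endpoint-level statements.

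**Working it through.** **Reproducing the plan's own figure.** Protocol 9.3, Table 1, gives an efficacy boundary of Z = 2.69640 at both looks. For a two-look Pocock boundary at half information, c solves P(Z1 > c or Z2 > c) = α*, where the correlation of Z1 and Z2 is √0.5. The one-sided α* = 0.025 gives c = 2.178, 0.025/2 gives 2.449, 0.025/3 gives 2.596 and 0.025/4 gives 2.6964. Only the last matches, so the design divides 0.025 equally over four hypotheses. The SAP gives no number for the final analysis now that there is one look. The single-look equivalent of 0.00625 is Z = 2.498, and that is the Bonferroni comparator used below.

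**The two procedures.**
- Bonferroni: reject any hypothesis with one-sided p ≤ 0.00625 (Z 2.498).
- Holm: order the p-values from smallest to largest and compare them with 0.025/4 = 0.00625, 0.025/3 = 0.00833, 0.025/2 = 0.0125 and 0.025 (Z 2.498, 2.394, 2.241, 1.960). Stop at the first failure.

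Holm keeps familywise error at 0.025 under any dependence. If m of the nulls are true, the first true null to be rejected must have p ≤ 0.025/m, and the sum over the m true nulls is at most 0.025. Its first step is the Bonferroni test, so the probability of at least one rejection is the same.

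**Inputs.** From SAP 4.1.2: virologic success 25% on placebo and 50% on active; clinical success 50% and 75%; allocation 1:1:1; 50 per arm at half information, hence 100 per arm at full information. From SAP 4.3: 68 patients, one look. Assumed, because the documents do not give them: the arm split (22, 23 and 23), no missing data, unadjusted pooled z-tests in place of the logistic models, and a latent correlation between endpoints of 0 to 0.5.

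**Check by formula, 100 per arm, virologic endpoint.** Pooled rate 0.375; null SE = √(2 × 0.375 × 0.625/100) = 0.0685; alternative SE = √((0.25 × 0.75 + 0.5 × 0.5)/100) = 0.0661. Power = Φ((0.25 − 2.498 × 0.0685)/0.0661) = Φ(1.19) = 88%. With the protocol's 2.6964 it is 84%. The clinical endpoint gives the same values by symmetry. Both agree with the stated target of more than 80%.

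**Simulation, all four effects real** (200,000 trials per setting; ranges are over the correlation; arrows run from Bonferroni to Holm):

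| Setting | At least one | At least two | All four |
|---|---|---|---|
| 68 patients, placebo arm is the 22 | 54-59%, same for both | 27% → 29% | 1-2% → 5-7% |
| 68 patients, a dose arm is the 22 | 53-57%, same for both | 25-26% → 30% | 1-2% → 5-8% |
| 100 per arm, single look | 99.5-99.8%, same for both | 97-99% → 98-99% | 65-67% → 85-86% |

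At 68 patients Holm adds at least one rejection in about 8-13% of trials. The gain for at least two rejections moves with the split because the outcomes are counts in small arms.

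**Only one endpoint real at both doses, or only one dose real on both endpoints, 68 patients.** Holm adds a rejection in 1-2% of trials when the placebo arm is the 22, and in up to about 3% when a dose arm is.

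**Checks.** Holm never lost a Bonferroni rejection in any simulated trial. With no effects, simulated familywise error at 68 patients was about 0.024 to 0.027 for both methods alike. The small excess over 0.025 comes from the normal approximation and not from the multiplicity procedure.

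**The case against.** Bonferroni delivers the error control that the plan promises, and the only conclusion that the plan defines does not change under Holm. No success criterion or power target exists for a second dose or a second endpoint. All of this stands. A reader might infer that the trial has a multiplicity error, or that it gives away its main conclusion. The documents support neither reading.

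A reader might also take the 100-per-arm row as the expected benefit. It is hypothetical: that trial was not completed, and its design had two looks at 2.69640. The 68-patient gain is modest, depends on the split, and is largest when all four effects are real. The SAP analysis is also a covariate-adjusted logistic regression with treatment interactions on observed data, so the simulated power is only indicative.

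Nor does Bonferroni lose power with nothing in return, because its simultaneous intervals agree with its tests. Finally, Holm loosens a protocol-specified rule after enrolment stopped. That is acceptable only if it is fixed and recorded before unblinding, which SAP 4.4 allows because authorisation of the SAP precedes it.

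The comparator of 2.498 is inferred. If the protocol's 2.69640 were still meant to apply, the first step would change too. The SAP does not say, which is a reason to state the level.

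**Conclusion.** The point holds as a matter of efficiency. Bonferroni over the four hypotheses is valid, and Holm at the same one-sided 0.025 rejects at least as much. With Bonferroni read as 0.00625 in a single look, the superiority claim and its power are unchanged.

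At 68 patients the benefit is about 2 to 5 points for at least two rejections and about 4 to 6 points for all four, provided all four planned effects are real, data are complete and the tests are unadjusted. If only one dose or endpoint works, the benefit nearly vanishes. No confirmatory claim per dose or per endpoint is defined, so what is forgone is power for additional statements and not a planned conclusion. Label: cheap improvement, not an error.

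**What to change.** Before unblinding:
- In SAP 8.4 and 14.1.1, state that the family is all four one-sided hypotheses (both doses, both endpoints). This also removes the difference between the two sections.
- State that the family is tested by Holm in a single look at 0.025/4, 0.025/3, 0.025/2 and 0.025.
- Define the one-sided p-value for each dose-versus-placebo contrast, because 14.1.1 now reports Type III Wald p-values with two-sided 95% intervals.
- Align the repeated sentence in SAP 4.1.2, and list the procedure in SAP 18 as a change from the protocol.

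The cost is a few sentences and no new data. The one drawback is that simultaneous intervals do not match Holm decisions one-to-one, so Bonferroni-level intervals should stay for estimation, with a note that they may include no difference where Holm rejects.
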